- ° Paraffin-embedded tumor tissue from primary or metastasis (excluding bone), for immunohistochemical studies to be conducted at a Sponsor specified CLIA certified laboratory. This is required for all non-clear cell histology subjects before Screening. Clear cell histology subjects must also provide tissue but at any point during the study. If no archive tissue is available; a biopsy may be performed to obtain tissue.
- ° Subjects are required to have a safety follow-up visit; refer to Section 5.2.7
- ° Physical exam, laboratory assessments, and ECOG assessment may be performed  $\leq$  4 days in advance of the subsequent Cycle Day 1.
- ° An Eye Symptom Questionnaire (ESQ) will be administered at every visit. Only subjects randomized to AGS-16C3F will have the ESQ done on PK only days. Refer to Section 5.6.5.1

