**5.1.1.2 Axitinib**

Axitinib will have a starting dose of 5 mg, administered twice daily continuously, by mouth. Refer to product label for details. Axitinib subjects will return to clinic every 21 days for clinical assessment and additional axitinib dispensing. If for logistical reasons (e.g., public holidays, clinic scheduling, etc.) the next clinic visit cannot occur 21 days from the last visit, a -2 day and a + 7 day visit window is allowed. This window is intended to accommodate occasional scheduling conflicts and is not intended for routine use. The Medical Monitor must be consulted for any study visit delays that are due to toxicity and for treatment hiatus that exceeds 5 weeks. Refer to Section [5.1.1.3](#)

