#### 5.2.6 Treatment Period

On C1D1, all procedures, other than post-infusion specific procedures, must be performed BEFORE first dose of study drug is administered and meet all inclusion and exclusion criteria.

During the treatment period, subjects who have a standard of care tumor biopsy or surgery, will have the opportunity to submit part of the sample for ENPP3 analysis. The subject will indicate their choice in the informed consent form.

##### 5.2.6.1 Cycles 1 – 4

All predose procedures below may be performed  $\leq 4$  days in advance of the actual dosing day, with the exception of the following which must be done on the dosing day:

- Vital signs
- ECG (C1D1 Only)
- Predose PK sample collection for AGS-16C3F subjects on Cycles 2-4. Predose PK sample for Cycles 2-4 must be collected anytime before AGS-16C3F drug administration on the day of infusion.
- Physical exam and body weight
- Vital signs; refer to Section 5.6.1
  - For AGS-16C3F Subjects: On the days of study drug administration, vital signs will be taken predose, and approximately 30 minutes after administration of study drug

- For axitinib Subjects: Vital signs will be taken once at each clinic visit
- ECG (C1D1 only); refer to Section 5.6.4
  - For AGS-16C3F Subjects: It will be done predose (anytime predose on actual dosing day) and 2 hours after the end of infusion, when the total prescribed dose has been administered (e.g., 2 h after the end of infusion), both in triplicate (approximately 3-5 minutes in between ECGs). Ensure that the subject is in the same position for every reading
  - For axitinib Subjects: ECG will be taken in triplicate (approximately 3-5 minutes in between ECGs) predose (anytime predose on actual dosing day). Ensure that the subject is in the same position for every reading
- ECOG Performance Status; refer to Appendix 12.5
- Hematology, chemistry, CRP, and PT/aPTT; refer to Section 5.6.3
- Thyroid Function Test, every odd cycle (e.g., Cycle 1, Cycle 3, etc.); refer to Section 5.6.3
- uPCR, every odd cycle (e.g., Cycle 1, Cycle 3, etc.); refer to Section 5.6.3
- Complete eye exam for AGS-16C3F subjects only will be done after the Cycle 2 Day 1 dose but before the Cycle 3 Day 1 dose, and as clinically indicated; refer to Section 5.6.5
- Complete ESQ at every scheduled and unscheduled visit; refer to Section 5.6.5.1
- PK and ADA blood samples will be collected for AGS-16C3F subjects only; refer to Table 1 and Table 2
- Disease assessment; refer to Section 5.5

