#### **5.6.5.1 Symptom Based Ocular AEs**

Ocular symptoms reported by the subject during clinic visits will be graded per CTCAE v4.03 (i.e., symptom based assessment) and this will guide the treatment decision for that visit and the necessity for a follow up ophthalmology consult.

An Eye Symptom Questionnaire (ESQ) will be administered at every visit in the oncology clinic. Please see the Study Guide for the form and for complete instructions. During screening, the ESQ will be completed for both Cancer Treatment History and Screening sections.

The ocular symptom AEs must be collected in the eDC system.

If a subject reports ocular symptoms, the following guidelines may be used:

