## **5.8 Test Drug Concentration**

Blood samples for the determination of serum AGS-16C3F concentrations will be collected according to [Table 2](#)

- Cycle 1, Day 1: predose (before the AGS-16C3F infusion), end of infusion (EOI), 4 hours, and Days 2 (24 hours), 4 (72 hours), and 15 (336 hours) post infusion
- Cycle 2, Day 22: predose (before the AGS-16C3F infusion)
- Cycle 3, Day 43: predose (before the AGS-16C3F infusion)
- Cycle 4, Day 64: predose (before the AGS-16C3F infusion), end of infusion (EOI), 4 hours, and Days 65 (24 hours), 67 (72 hours), and 78 (336 hours) post infusion
- Cycle 6, Day 106: predose (before the AGS-16C3F infusion)

Blood sampling, processing, storage and shipment instructions will be provided in the Lab Manual. Samples will be shipped to and analyzed by a Sponsor designated analytical laboratory. Please refer to the Lab Manual for more detailed information.

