19.7.2. EYE SYMPTOM QUESTIONNAIRE

The Eye Symptom Questionnaire (ESQ) will be completed at screening and on other occasions when the full ophthalmologic exam is performed. The ESQ collects information related to the following items:

- Dry Eyes (none, mild, moderate, severe)
- Eye Pain (none, mild, moderate, severe)

- Blurred Vision (none, mild, moderate, severe)
- Photophobia (none, mild, moderate, severe)
- Other, specify (none, mild, moderate, severe)
- Steroid Use (Taken as directed, used most of the time, did not use most of the time, used every day continuously, did not use at all, other)

A summary table by treatment arm will present the number and percentage of subjects who reported each eye symptom, overall and by severity, during each cycle and at the Safety Follow-up visit. Each unique symptom report will be counted only in the cycle in which it began. The severity of the worst post-baseline assessment and the final assessment will also be tabulated. A data listing will be provided.

A separate table will display the number and percentage of subjects who had >25%, >50%, >75%, or 100% of ocular symptom-free days during treatment. The calculated number and percentage of symptom-free days by subject will be provided in a listing.

Also, a swimmer lane plot which shows the duration of any post-baseline ocular symptom during the period from Day 1 through the end of the Safety Follow-up period will be produced. The plot will display a bar connecting any consecutive visits at which a symptom was reported, or a simple bracket or narrow line around individual visits at which a symptom was reported. Important treatment events (e.g., day of first dose, day of last dose or decision to end treatment, day of Safety Follow-up visit, day of each study drug infusion for AGS-16C3F subjects) will be marked on the subject's timeline.

A summary of ocular steroid use by cycle and at the final assessment will be produced.

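### Six eye-symptom questionnaires in Cycles 1 and 4 are scheduled only in the AGS-16C3F arm, so the Cycle 1, Cycle 4 and worst-post-baseline comparisons with axitinib can be inflated

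*Protocol*

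**What the plan says.** Protocol 5.6.5.1 states: "An Eye Symptom Questionnaire (ESQ) will be administered at every visit in the oncology clinic". Section 5.2.6 extends this to unplanned contacts: "Complete ESQ at every scheduled and unscheduled visit".

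The ESQ row of Protocol Table 1 is marked for both arms at screening, on Days 1, 22, 43, 50-57, 64, 85 and 106, every three weeks from Cycle 7, and at Safety Follow-Up. The marks on Days 2, 4, 15, 65, 67 and 78 carry a footnote: "Only subjects randomized to AGS-16C3F will have the ESQ done on PK only days". Section 5.8 confirms that these are the drug-concentration sampling days: "Days 2 (24 hours), 4 (72 hours), and 15 (336 hours) post infusion" in Cycle 1 and "Days 65 (24 hours), 67 (72 hours), and 78 (336 hours) post infusion" in Cycle 4. The axitinib arm keeps the three-weekly rhythm; Section 5.1.1.2 says "Axitinib subjects will return to clinic every 21 days for clinical assessment and additional axitinib dispensing".

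SAP 19.7.2 then plans the comparison: "A summary table by treatment arm will present the number and percentage of subjects who reported each eye symptom". This is done overall and by severity, per cycle and at Safety Follow-Up, with each new report credited to the cycle in which it started. Worst post-baseline severity, the final assessment and a table of symptom-free days are added. Nothing limits these tables to visits that both arms have, or allows for the number of questionnaires. On collection, the same section says that the ESQ is completed at screening and "on other occasions when the full ophthalmologic exam is performed".

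**The concern.** A subject who is asked more often has more chances to report a symptom. Where one arm is asked more often by design, part of any difference in the percentage reporting, or in worst severity, can come from the schedule.

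The matter is not peripheral here. Protocol 1.4 names ocular toxicity as the compound's main distinctive toxicity, safety against axitinib is a secondary objective (Protocol 2.1.2), and SAP 2.3 lists ocular safety as an objective. The tables are descriptive, but percentages in adjacent columns will be read as a comparison.

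The collection sentence in the SAP is a second problem, and it needs no assumption. Protocol 5.6.5 schedules no post-baseline eye exam for axitinib; exams there are done only when clinically indicated. Read literally, SAP 19.7.2 would leave axitinib with no scheduled post-baseline ESQ. That conflicts with the protocol, and also with the by-cycle table that the same SAP section asks for.

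**Working it through.** The documents state no ESQ count or ratio, so there is no figure to reproduce.

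**Step 1: count the marks in Table 1.** Common to both arms after C1D1: Days 22, 43, 50-57, 64, 85 and 106, which is 6. AGS-16C3F only: Days 2, 4, 15, 65, 67 and 78, which is 6. So 6 + 6 = 12 against 6, a ratio of 2.00.

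| Period | AGS-16C3F | Axitinib |
|---|---|---|
| Cycle 1, with Day 1 | 4 | 1 |
| Cycle 1, post-dose | 3 | 0 |
| Cycle 2 | 1 | 1 |
| Cycle 3 | 2 | 2 |
| Cycle 4 | 4 | 1 |
| Cycle 5 | 1 | 1 |
| Cycle 6 | 1 | 1 |
| Cycle 7 on | equal | equal |

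The Day 1 questionnaire is not post-dose, because Protocol 5.2.6 puts C1D1 procedures before the first dose. The next scheduled axitinib ESQ is on Day 22, a Cycle 2 visit.

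**Step 2: longer follow-up.** The excess stays at six while common visits accumulate every 21 days from Day 127. At equal time on treatment the ratio is 15/9 = 1.67 at 6 months, 19/13 = 1.46 at 9 months and 24/18 = 1.33 at 12 months. The Phase 1 median treatment duration at 1.8 mg/kg (Protocol 1.4) was 17.7 weeks, and 17.7 × 7 = 123.9 days. This falls before Day 127, so the count is still 12 to 6 there, leaving aside Safety Follow-Up.

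**Step 3: effect on the percentage with any report by Day 106, with identical true symptoms in both arms.** Prevalence, episode length and the ESQ recall period are not in the documents, so these are assumptions.

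*Independent reports,* probability q at each ESQ, 1 − (1 − q)^k:
- q = 5%: 1 − 0.95^12 = 46.0% against 1 − 0.95^6 = 26.5%, ratio 1.74.
- q = 10%: 1 − 0.90^12 = 71.8% against 1 − 0.90^6 = 46.9%, ratio 1.53.

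*Symptoms that persist.* A two-state daily Markov process was simulated for 100,000 subjects, symptom-free on Day 1 and read on each arm's ESQ days (Day 57 for the week 8-9 visit), with no recall beyond the day:

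| Mean episode | Prevalence 5% | Ratio | Prevalence 15% | Ratio |
|---|---|---|---|---|
| 3 days | 39.1% vs 26.3% | 1.49 | 79.8% vs 61.9% | 1.29 |
| 7 days | 31.5% vs 24.4% | 1.29 | 70.9% vs 59.6% | 1.19 |
| 21 days | 17.8% vs 16.1% | 1.11 | 48.2% vs 44.1% | 1.09 |
| 60 days | 8.0% vs 7.6% | 1.05 | 24.2% vs 23.3% | 1.04 |

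*Full recall since the last visit.* The any-time difference by Day 106 is 0.

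**Step 4: the affected rows.** At 5% prevalence and 7-day episodes, the share with a positive ESQ in Cycle 4 is 10.8% against 4.9%. In Cycle 1 post-dose it is 6.3% on AGS-16C3F, with no scheduled axitinib reading. These figures count any positive ESQ in the cycle; the SAP row counts reports that began in it. Under the SAP rule, a symptom first caught on a PK-only day is credited to Cycle 1 or 4 and not to the following cycle, so rows with equal counts can shift slightly too.

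**Step 5: after restriction to common visits.** The count is 6 against 6, and the schedule-driven difference is 0 under equal true rates. Neither arm then has a scheduled post-dose ESQ in Cycle 1.

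**The case against.** Several stronger readings are tempting, and the documents do not support them.

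- *AGS-16C3F subjects are asked twice as often throughout.* True only after C1D1 to Day 106. The excess is a fixed six in two cycles, and most rows of the by-cycle table have equal scheduled counts.
- *Axitinib incidence in Cycle 1 is zero by design.* Only the scheduled post-dose ESQ is missing. ESQs are also completed at unscheduled visits in both arms, and a symptom reported on Day 22 could be credited to Cycle 1 if the form records onset. The items listed in SAP 19.7.2 show no onset date, but the form itself is in the Study Guide.
- *The tables must overstate the difference.* This depends on recall and episode length. Independence is least plausible for questionnaires a day or two apart, so the 5% and 10% figures sit towards the upper end. With Phase 1 ocular toxicity in 12 of 13 subjects at this dose, the AGS-16C3F percentage may also be near its ceiling.
- *Symptom-free days are biased against AGS-16C3F.* No calculation rule is given. If the swimmer-plot convention of joining consecutive positive visits were borrowed, an axitinib subject positive on Days 64 and 85 would be joined across the gap. An AGS-16C3F subject negative on Days 65, 67 and 78 would not. The direction cannot be settled from the documents.

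Three further objections carry weight. SAP 19 plans no between-arm tests of safety data unless specified, and ocular events also appear in the adverse event and eye-exam tables, so closer questioning would not hide harm. The SAP does not say outright that every questionnaire is used; that is inferred from the absence of a restriction. The SAP is also written against protocol version 4.0, which may explain its collection sentence, though it still has to agree with the current protocol.

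The unequal schedule in Cycles 1 and 4 stands, as does the lack of any allowance for it.

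**Conclusion.** The concern holds in a limited form. The asymmetry is a matter of record: 12 against 6 scheduled ESQs after C1D1 to Day 106, all of the excess in Cycles 1 and 4. Under equal true rates it can raise the AGS-16C3F figures in the Cycle 1, Cycle 4 and worst-post-baseline rows.

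The any-report ratio runs from 1.0 with full recall, through about 1.04 to 1.49 for mean episodes of 60 to 3 days, to about 1.7 for independent reports at 5%. These figures rest on assumed prevalence and duration, on no recall beyond the day (except the 1.0), and on equal time on treatment. No claim is made about symptom-free days.

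No test or error rate is affected. This is a cheap improvement to the presentation of the drug's main toxicity, together with a contradiction between SAP and protocol that has to be resolved.

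**What to change.** In SAP 19.7.2:

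1. Base the between-arm incidence and worst-severity comparison on ESQs at visits scheduled for both arms: Day 1 of each cycle, the week 8-9 visit and Safety Follow-Up. Assign the starting cycle from those questionnaires alone.
2. Label Cycle 1 as not comparable between arms.
3. Keep the all-questionnaire table, including PK-only-day reports, as the safety description of AGS-16C3F, and show the number of ESQs per arm and cycle.
4. State how symptom-free days are calculated.
5. Reconcile the collection sentence with the protocol's rule that the ESQ is done at every visit.

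The cost is a visit filter, one further table and some SAP text; no new data are needed. If outputs already exist, Protocol Section 7 allows a change from the SAP to be justified in the study report. The downside is that transient symptoms seen only on PK-only days leave the comparative table, but they stay in the all-questionnaire table, so no observed report is lost.

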## VI. PK SAMPLING COLLECTION SCHEMA

**Table 2 AGS-16C3F PK Sampling Time Points**

Cycle	Study Day	Time	Window
1	1	Predose	Anytime Predose *
		EOI	Within 2 min after EOI
		4 h †	± 15 min
	2	24 h from Day 1 †	± 4 h
	4	72 h from Day 1 †	± 1 day
	15	336 h from Day 1 †	± 4 h
2	22	Predose	Anytime Predose §
3	43	Predose	Anytime Predose §
4	64	Predose	Anytime Predose §
		EOI	Within 2 min after EOI
		4 h †	± 15 min
	65	24 h from day 64 †	± 4 h
	67	72 h from day 64 †	± 1 day
	78	336 h from day 64 †	± 4 h
6	106	Predose	Anytime Predose §
Q12W (starting at C6)		Predose	Anytime Predose §

\* May be performed ≤ 4 days in advance of C1D1

† timepoints are from end of infusion, when the total prescribed dose has been administered (e.g., 4 h after the end of infusion)

§ Anytime predose on the actual day of AGS-16C3F administration

## 1 INTRODUCTION

### 1.1 Background

#### 1.1.1 Disease

Renal cell carcinoma (RCC) accounts for 2% to 3% of all malignant diseases in adults. It is the seventh most common cancer in men and the ninth most common in women.

Historically, treatment has focused primarily on nephrectomy, followed by nonspecific immunotherapy, and sometimes radiation therapy. Nonspecific immunotherapy includes treatment with the cytokines interleukin-2 or interferon-2 $\alpha$ , as either single agents or in combination (Beldegrun et al, 2008). After surgical excision, 20-30% of patients will develop metastatic disease within 1-3 years, often in the lung (Motzer, 2011). Median survival for patients with metastatic disease is approximately 13 months (Ljungberg et al, 2010).

Since 2005, 10 agents have been approved in the United States and other world regions for the treatment of advanced RCC: sorafenib (Nexavar®), sunitinib (Sutent®), temsirolimus (Torisel®), everolimus (Affinitor®), bevacizumab (Avastin® in combination with interferon alpha), pazopanib (Votrient®), axitinib (Inlyta®), cabozantinib (Cabometyx®), lenvatinib (Lenvima® in combination with everolimus), and nivolumab (Opdivo®). These drugs target specific pathways important in RCC, including angiogenesis and mTOR signaling, or act as a checkpoint inhibitor, allowing the immune system to fight the cancer. Their use was shown mostly to affect response rate and/or duration.

While these drugs which either block the vascular endothelial growth factor (VEGF) pathway, inhibit mammalian target of rapamycin (mTOR), or block the signal that prevents activated T cells from attacking the cancer have significantly increased both treatment options and improved outcomes for patients with advanced RCC, the vast majority still relapse.

The recent advances in treatment options mainly affected patients with clear cell histology, while no real progress has been made in those with other histologies.

A novel mechanism of action drug to treat advanced RCC of all histologies with a different treatment approach is much desired.

#### 1.1.2 Agensys Antibody Drug Conjugate against Renal Cell Carcinoma

AGS-16C3F, an antibody drug conjugate (ADC) developed by Agensys, is comprised of a chinese hamster ovary (CHO) cell line-derived antibody against ENPP3, conjugated to monomethyl auristatin F (MMAF), a microtubule disruptive agent. A Phase 1 study was conducted to evaluate the pharmacokinetics and safety of AGS-16C3F administered monotherapy in metastatic RCC subjects. This Astellas Phase 2 study is planned based on the results of the Phase 1 study. Results from the Phase 1 study are pending full data analysis.

#### 1.1.3 ENPP3 Antigen Target and Expression in Cancer

The antigen target, ENPP3 (referred to as AGS-16), was cloned from a patient renal carcinoma specimen and identified as an 875 amino acid type II single transmembrane

antigen that is upregulated in the majority of renal and in a subset of hepatocellular cancers. Sequencing of AGS-16 identified it as ENPP3 (CD203c), one of 7 members of a family of cell surface ectonucleotide phosphodiesterases-pyrophosphatases (PDEs), ENPP1-7 (Deissler et al, 1995) (Jin-Hua et al, 1997) (Buhring et al, 2001) (Goding et al, 2003) (Stefan et al, 2005). The physiological substrate of ENPP3 is unknown, but studies have suggested that the enzyme catalyzes extracellular nucleotides (e.g., ATP; Goding et al, 2003).

Immunohistochemical (IHC) and tissue cross reactivity studies have shown restricted expression of ENPP3 in normal tissues predominantly in a subset of cells in the kidney cortex. Low levels of staining were also observed in the epithelium of the fallopian tube, a subset of cells within gastrointestinal tract epithelium, in uterine endometrium, parotid gland, and the cortex of the thymus. Flow cytometric analysis has also shown that ENPP3 is expressed on activated basophils and mast cells (Buhring, 1999). ENPP3 is highly expressed in approximately 90% renal clear cell carcinoma; 69% papillary RCC and 27% hepatocellular carcinoma as determined at Agensys by staining tissue microarrays with an immunohistochemistry antibody specific for ENPP3.

## 1.2 Non-clinical and Clinical Data

### 1.2.1 Antibody Drug Conjugate AGS-16C3F Non-clinical Pharmacology

AGS-16C3F is comprised of a fully human IgG2k mAb, following conjugation with the cytotoxic drug MMAF via a non-cleavable maleimidocaproyl (mc) linker. MMAF is a synthetic analog of the naturally occurring tubulin-binding drug, dolastatin 10, that was modified to contain a charged C-terminal phenylalanine residue (Doronina et al, 2006) (Pettit, 1987). Conjugation takes place on cysteine residues that comprise the interchain disulfide bonds of the antibody to yield a product with a target drug to antibody ratio of 4.0 + 0.5.

AGS-16C3F binds specifically to ENPP3 (AGS-16) expressed on the surface of renal, hepatocellular and chronic myelogenous leukemia (CML) cells with high affinity (Kd = 0.54 nM). Following binding to cell surface ENPP3, AGS-16C3F is internalized and trafficked through the endocytic pathway to the lysosomes where catabolism results in release of cysteine adducts of mcMMAF that subsequently bind to and inhibit microtubules (Sutherland et al, 2006).

The mechanism of action and catabolism of AGS-16C3F is similar to that of other mAbs conjugated with non-cleavable linkers (Polson et al, 2009) (Oflazoglu et al, 2008) (Erickson et al, 2006). These ADCs have the potential to yield an excellent therapeutic index due to increased stability of the non-cleavable linker in circulation and impaired cellular access of the charged metabolic products produced intracellularly (Alley et al, 2009) (Doronina et al, 2006). The pharmacologic data collected for AGS-16C3F demonstrate that it binds with high affinity to both human and cynomolgus monkey ENPP3 and that it does not cross react with other ENPP family members. Moreover, treatment with AGS-16C3F produces potent cellular cytotoxicity in vitro and regression or long term growth inhibition of well-established tumors in vivo.

AGS-16C3F inhibited tumor growth in 3 different ccRCC xenograft models. While AGS-16M8F, the hybridoma cell line-derived version of the same ADC studied earlier, was shown to bind to basophils from human and monkey, *in vitro* experiments showed no histamine release upon incubation of human or cynomolgus monkey blood with AGS-16M8F. Moreover, there were no signs of allergic reactions to AGS-16M8F in cynomolgus monkeys treated with doses up to 6 mg/kg/week for 4 weeks. Likewise, no overt kidney toxicities were observed.

Please refer to the confidential AGS-16C3F Investigator's Brochure for further details.

